7.5.3 Accountability

The Investigator at each site is responsible for IP supplies. The Investigator will ensure that adequate records of the receipt, dispensing, and return of the IP are kept and that the IP is used only for subjects enrolled in the study. All data regarding the IP must be recorded on the relevant forms provided.

Each study site will maintain a drug inventory/dispensing record for all IP dispensed and returned. At the end of the study, one copy of the drug inventory/dispensing record should be sent to Aurinia or designee for the central study file. The original will be kept in the site files.

After completion of the study, or if it is prematurely terminated, all undispensed IP will be returned to Aurinia. The decision to destroy IP at a site must be made by Aurinia. If the dispensed/returned IP is destroyed at a site, the Investigator must receive Aurinia approval of the site's standard operating procedure addressing the destruction process and forward documentation of destruction to Aurinia.

7.6 Procedures for Overdose

Preclinical findings suggest that systemic effects from an overdose are unlikely, as the peak blood levels after ocular instillation are below those achieved with oral doses of voclosporin.

Based on clinical experience with voclosporin, symptomatic treatment of AEs is indicated. In the event of overdose, discontinuation of treatment should be considered.

7.7 Prohibited Therapy and Concomitant Treatment

Any concomitant treatment given for any reason during the study must be recorded in the eCRF and in the subject's source documents, including dosage, start and stop dates, and reason for use.

Any class of medications not mentioned in [Section 7.7.1](#), Prohibited Medications and with the potential to interfere with evaluation of the study treatment must be discussed and documented with the Medical Monitor.

7.7.1 Prohibited Medications

The following drugs/therapies shall be prohibited during the study and for the timeframes specified below: A subject should not have received:

- any investigational drug or device within 30 days prior to the Screening Visit (Visit 1) and may not receive any investigational drug or device during the entire study except that which is allowed by the protocol

- Ophthalmic drugs (any topical eye medications) including prescription medication and OTC agents, except IP and study lubricant at Visit 1 and Visit 2, from Visit 1 to Visit 6.
- Contact lenses during the period from the Screening Visit (Visit 1) to the end of the study (Visit 6)
- Prohibited Medications:
 - Any prior use of amiodarone
 - Within 14 days prior to study and for the duration of the study:
 - Xiidra[®] (lifitigrast)
 - Within 30 days prior to study and for the duration of the study:
 - Restasis[®] (cyclosporin ophthalmic emulsion); NOTE: Any prior use of Restasis[®] may not have exceeded 1 month of continuous use
 - Topical ocular antihistamines
 - Ocular, inhaled or intranasal corticosteroids
 - Topical or oral mast cell stabilizers
 - Oral antihistamines
 - Topical or nasal vasoconstrictors
 - Topical ocular nonsteroidal anti-inflammatory drugs (NSAIDs)
 - Topical ocular antibiotics
 - Within 30 days prior to the screening visit (Visit 1) or during the study alteration to the dose or anticipated alterations to the dose of the following are disallowed:
 - Tetracyclines
 - Omega 3s or Omega 6s
 - Within 60 days prior to the screening visit (Visit 1) or during the study alteration to the dose or anticipated alterations to the dose of the following are disallowed:
 - Anticholinergics

- Antidepressants
 - Oral contraceptives
 - Isotretinoin
 - Oral systemic corticosteroids
 - Oral systemic immunosuppressive agents
- Within 90 days prior to the screening visit (Visit 1) or during the study, in the study eye has had cauterization of the punctum or alternations to (insertion or removal) punctal plug(s) or nasolacrimal surgery. Note: If a Punctal Plug is in place at screening visit (Visit 1) and it is dislodged during the study, the plug should be replaced as soon as possible
 - At screening visit (Visit 1) or any time throughout the study:
 - Chronic oral anti-viral medications for ocular herpetic disease

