4. INVESTIGATIONAL PLAN

4.1 Overall Study Design

This is a Phase 2, multi-center, Investigator-masked, randomized, parallel-group study to evaluate the tolerability, efficacy and safety of VOS versus Restasis[®] over a 28-day treatment period in subjects with mild to moderate DED. Approximately 90 subjects will be randomized to either VOS or Restasis[®] at approximately 7 centers located in the US.

At Visit 1 (screening), informed consent will be obtained from subjects and eligibility will be determined. A STT will be performed at this visit. The score will be used for eligibility and baseline. During this visit, all subjects will self-administer an OTC ocular lubricant, Refresh Plus[®], OU to assess ability to self-administer study product.

At Visit 2 (Randomization), continued eligibility will be confirmed. During this visit, all subjects will self-administer an OTC ocular lubricant, Refresh Plus[®], OU to evaluate ability to tolerate ocular drops. Individuals who are unable to successfully instill the drops or who rate OTC ocular lubricant as uncomfortable, based on a post-instillation Drop Discomfort VAS score, will not be eligible for participation in the study. (Note: For subjects meeting the Screening and Randomization Criteria, the Visit 2 Drop Discomfort VAS score will be used as the baseline value.)

Eligible subjects will be randomly assigned in a 1:1 ratio to one of the two treatment groups: VOS BID or Restasis[®] BID. The first instillation of Investigational Product (IP) will be administered, at least 2 hours following administration of Refresh Plus[®] and by clinic personnel to both eyes during Visit 2. IP will be administered to the subject by an unmasked dedicated dosing coordinator (the subject and the Investigator will be masked to study treatment for the first post randomization instillation). Tolerability, safety and efficacy assessments will be performed at this visit.

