5.2 Inclusion Criteria

At Visit 1 and Visit 2 (as specified in the Schedule of Events), subjects may be eligible for participation if they:

1. Provide written informed consent before any study-specific procedures are performed.
2. Are male or female subjects with a minimum age of 18 years (or legal age of consent if >18 years), at the time of screening (Visit 1).
3. Are willing and able to follow instructions and can be present for the required study visits for the duration of the study.
4. Have a BCVA in both eyes of +0.7 logarithm of the Minimum Angle of Resolution (logMAR) or better as assessed by Early Treatment of Diabetic Retinopathy Study (ETDRS) chart at Visit 1.
5. Have a documented history of DED in both eyes supported by a previous clinical diagnosis at Visit 1.
6. Have ongoing DED, as defined by at least one eye (if one eye, the same eye) meeting all the following criteria:
 - A symptom severity score of ≥ 30 for Eye Dryness on the Individual Symptom Severity Assessment VAS (0-100) at Visit 2
 - An unanesthetized STT score of ≥ 1 mm and ≤ 10 mm per 5 minutes (Note: STT Score obtained at Visit 1)
 - Evidence of ocular surface staining (total fluorescein staining score of at least 3 [0-15 scale]) at Visit 2
7. Have normal lid anatomy at Visit 1.

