8.1.1.4 Unanesthetized Schirmer Tear Test (STT)

Schirmer Tear Test (without anesthesia) will be conducted at Visit 1, Visit 4 and Visit 5. This procedure should be conducted at least 1 hour following administration of IP and at least 20 minutes following FCS at Visit 4 and Visit 5:

Identical Schirmer strips will be supplied to each site. When conducting assessments room temperature and humidity should be relatively consistent throughout each visit and throughout the study.

- While still in the plastic sheath, fold the notched end of the Schirmer strip at the apex of the “v.” Additionally, make a partial second fold at the halfway point of the strip so that the strip does not lie directly in the subject’s line of sight
- Remove the right eye strip from the sheath
- Ask the subject to look up and gently draw the right lower lid in a downward and temporal direction

- Place the rounded end of the strip toward the temporal one-third of the lower eyelid
- Repeat this procedure in the left eye
- Darken the room but ensure that the largest letter(s) of a Snellen or ETDRS chart is visible
- Instruct the subject to relax and look at the chart while blinking normally or have patients gently close eyes
- Remove the strips after 5 minutes
- After removing the strips, with a sharp pencil draw a horizontal line across the leading edge of moisture and a second horizontal line across the lowest point of moisture
- Using a ruler and/or the millimeters recorded on the strips, measure a point halfway between the two lines and record this as the amount of wetting

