8.2 Schedule of Assessments

A detailed schedule of assessments (including all protocol-required assessments, visits, and visit windows) is located on the Schedule of Events ([Table 1](#)). No study-related assessments will be performed (including changes to current medications to meet study eligibility) until the subject has provided signed and dated informed consent. Every effort will be made to keep the subject within the requested visit schedule. If a subject is seen outside of the visit window listed on the Schedule of Events, the reason must be clearly documented in the source notes.

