8.2.1 Screening Procedures

8.2.1.1 VISIT 1

The screening visit will take place within 3 days prior to Visit 2. After obtaining informed consent, site staff will perform/assess the following procedures in the order below. There will be a collection of information including:

- Demographics
- Prior documented DED diagnosis
- Ocular, general medical and surgical history
- Concomitant medication history
- UPT for all eligible WOCBP
- BCVA assessment
- Unanesthetized STT
- Dilated Ophthalmoscopy
- Assessment of ocular lubricant self-instillation
- AE assessment

- Inclusion and exclusion criteria assessment: Subjects who do not meet the evaluated criteria will not continue participation in the study. Any subject who does not meet eligibility requirements will be considered a Screen Failure.

Subjects should be reminded not to use artificial tears or any other OTC or prescription or any other topical eye medication except for the IP for the duration of their participation in the study.

Subject will be scheduled to return for Visit 2 in one to three days.

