7.0 STATISTICAL ANALYSIS

All statistical analyses and reporting will be performed using the SAS® System Version 9.4 or later.

Unless otherwise specified, continuous variables will be summarized with descriptive statistics (n, mean, median, standard deviation, standard error, minimum, and maximum), and categorical variables will be summarized with counts and percentages.

7.1 Calculation of Study Day:

Study day will be calculated as the number of days from first dose of study drug (Day 1):

- Date of event – date of first dose of study drug + 1, for events on or after first dose
- Date of event – date of first dose of study drug, for events before first dose

To this end, Day 0 remains undefined.

Definition of Baseline:

Study day will be calculated as the number of days from first dose of IP/study drug (Day 1). Baseline measurements will be the last measurement for the corresponding variable prior to the first randomized dose on Day 1.

Out of Window and Unscheduled Visits:

The protocol defined windows for scheduled visits will not be used in the analyses by visit. Data will be assigned to the scheduled visit closer in time to the actual visit. Unscheduled visit data will only be used in an analysis if there are no other available data closer in time to a scheduled visit. All unscheduled visit data will be included in data listings.

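### The Visit 1 Schirmer test is the only STT baseline and sets STT eligibility, but no minimum interval separates it from the subject's own eye drops, and the Protocol and SAP disagree on whether it precedes dilation

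*Protocol*

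**What the plan says.** **Role of the Visit 1 test.** Protocol 8.1.1.4: "Schirmer Tear Test (without anesthesia) will be conducted at Visit 1, Visit 4 and Visit 5". Protocol 5.2 requires a score from 1 to 10 mm per 5 minutes at Visit 1, and Protocol 4.1 says of that score: "The score will be used for eligibility and baseline". SAP 7.1 adds the general rule: "Baseline measurements will be the last measurement for the corresponding variable prior to the first randomized dose on Day 1". With no STT at Visit 2, only the Visit 1 value can satisfy it.

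**Own drops.** Protocol 7.7.1 prohibits topical eye products, "including prescription medication and OTC agents, except IP and study lubricant at Visit 1 and Visit 2, from Visit 1 to Visit 6". The same section gives 14 days for lifitegrast and 30 days for Restasis and several other topical classes, but nothing before Visit 1 for artificial tears. The instruction to stop follows the Visit 1 procedure list in Protocol 8.2.1.1: "Subjects should be reminded not to use artificial tears or any other OTC or prescription". Protocol 8.2 allows no study-related assessments, "including changes to current medications to meet study eligibility) until the subject has provided signed and dated informed consent".

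**Later visits.** For Visits 4 and 5, Protocol 8.1.1.4 states: "This procedure should be conducted at least 1 hour following administration of IP and at least 20 minutes following FCS".

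**Order at Visit 1.** Protocol 8.2.1.1 prescribes an order in which STT comes after BCVA and before dilated ophthalmoscopy and the study lubricant. SAP 3.1.4 puts STT before the lubricant but after dilated ophthalmoscopy, and attributes that order to the protocol.

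**The concern.** A Schirmer strip takes up whatever fluid is on the eye. If a subject used tears shortly before the Visit 1 test, or if dilating drops went in first, the reading may include instilled fluid. The plan guards against this at Visits 4 and 5 by stating intervals, and at Visit 1 it guards against the study lubricant by placing STT first. It leaves the subject's own drops uncontrolled at the one visit whose STT value cannot be replaced.

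Several things depend on that value. These are the 1 to 10 mm eligibility window, the key secondary change from baseline at Visits 4 and 5, all four exploratory responder endpoints, the choice of the worst-STT eye for those endpoints (SAP 7.5.4), and the baseline covariate in both the ANCOVA (SAP 7.6.1) and the logistic model (SAP 7.6.2). SANDE, the symptom VAS and corneal staining have their baselines at Visit 2, after the ban has begun, so STT is the only efficacy baseline exposed in this way.

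**Working it through.** The plan gives no figure for this point, so there is none to reproduce. The check has two parts.

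**1. Does any passage set the interval?**

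| Possible safeguard | What it provides for the Visit 1 STT |
|---|---|
| Protocol 7.7.1, topical products | Ban starts at Visit 1; no hours or days beforehand |
| Exclusion 13 | Bars those taking Section 7.7 therapies at Visit 1; takes its timeframes from 7.7, so adds no interval for tears |
| Protocol 8.2.1.1, reminder | Placed after the procedure list |
| Protocol 8.2.1.1, order | Consent, history and BCVA come first: some delay, no stated minimum |
| Protocol 8.1.1.4, 1 hour and 20 minutes | Visits 4 and 5 only |
| SAP 3.1.4 | Order only, and it conflicts with the Protocol on dilation |

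None does.

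**2. How large could the effect be?** All inputs here are assumptions; none is in the documents.

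- Change in STT is Normal with mean 2 mm and SD 5 mm.
- A share f of screened subjects have residual fluid that adds d mm at Visit 1.
- True Visit 1 STT is uniform from 0 to some value of at least 10 mm.
- One eye per subject is modelled. The protocol needs only one qualifying eye, so this is a simplification.

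The 1 to 10 mm rule acts on the observed score. Unaffected subjects enter if true STT is 1 to 10, a width of 9. Affected subjects enter if true STT is 0 to 10 − d, a width of 10 − d. The affected share among those enrolled is therefore

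g = f(10 − d) / [f(10 − d) + 9(1 − f)].

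Then:

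- fall in mean change = g·d
- responder rate at cut c = (1 − g)·P(change ≥ c) + g·P(change ≥ c + d)
- unadjusted SE factor = √[1 + g(1 − g)d²/25]
- truly eligible subjects rejected = f·d/9
- enrolled with true STT below 1 mm = f/[f(10 − d) + 9(1 − f)]

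Normal tail values: P(Z ≥ 0.6) = 0.274, P(Z ≥ 1) = 0.159, P(Z ≥ 1.6) = 0.055, P(Z ≥ 2.6) = 0.005.

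*Low case, f = 0.1, d = 2.*
- g = 0.8/(0.8 + 8.1) = 0.090; fall = 0.090 × 2 = 0.18 mm.
- 5 mm rate = 0.910 × 0.274 + 0.090 × 0.159 = 26.4%, against 27.4% without contamination.
- SE factor = √(1 + 0.090 × 0.910 × 4/25) = 1.007.
- Rejected: 0.1 × 2/9 = 2.2%. Below the floor: 0.1/8.9 = 1.1%.

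*Higher case, f = 0.3, d = 5.*
- g = 1.5/(1.5 + 6.3) = 0.192; fall = 0.192 × 5 = 0.96 mm.
- 5 mm rate = 0.808 × 0.274 + 0.192 × 0.055 = 23%.
- 10 mm rate = 0.808 × 0.055 + 0.192 × 0.005 = 4.5%, against 5.5%.
- SE factor = √(1 + 0.192 × 0.808) = 1.07.
- Rejected: 0.3 × 5/9 = 16.7%. Below the floor: 0.3/7.8 = 3.8%.

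If half of screened subjects were affected at d = 5, g = 2.5/7 = 0.357 and the fall would be 1.8 mm. Nothing in the documents makes so large a share likely.

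**Planned analysis.** SAP 7.6.1 uses ANCOVA with baseline as a covariate. ANCOVA of change adjusted for baseline gives the same treatment estimate as ANCOVA of the follow-up value adjusted for baseline. Contamination then costs precision only by weakening the relation between baseline and follow-up, so the unadjusted SE factors overstate the loss for that analysis. The Wilcoxon fallback, being unadjusted, gets no such relief.

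**The case against.** The other side has real points.

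- Section 7.7.1 excepts only study product and the study lubricant at Visit 1, and Exclusion 13 refers to therapies being taken at Visit 1. Together they can be read as covering the day of Visit 1. That reading stands as possible, but it yields no number of hours, and sending subjects back to their prior ocular therapy at Visit 6 (Protocol 8.2.5.1) suggests that users of eye products were expected to enrol.
- Consent, histories and BCVA precede STT, so some time always passes, and the medication history gives staff a chance to learn of recent drops. This stands, and it makes large residual volumes less likely. It is still not a stated minimum.
- The 1-hour and 20-minute intervals exist because study product and fluorescein are instilled at Visits 4 and 5. In the Protocol's Visit 1 order no study drop precedes STT. This is fair, but under the SAP's order dilating drops would precede it.
- The 1-hour figure is borrowed from study product; the documents do not support it specifically for artificial tears.

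A reader might cite the 2-hour gap between Refresh Plus and the first study dose as further evidence that the plan regards recent drops as distorting STT. It does not show that: the gap separates two discomfort ratings for the primary endpoint. A reader might also infer that baseline strips will typically be taken soon after tears. The documents leave this possible but do not say how often it would happen.

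**Conclusion.** The gap is real and modest. The Visit 1 STT has no stated minimum interval from the subject's own drops, and the two documents contradict each other on its order relative to dilation. The second finding needs no assumption about subjects' habits.

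The damage is confined to noise in the STT baseline, some eligibility misclassification, possible change of the worst-STT eye where residual fluid differs between eyes, and understated within-arm change and responder rates. Its size cannot be derived from the documents. Under the assumed inputs with up to 30% of screened subjects affected, the loss in mean change is negligible to about 1 mm.

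Two stronger readings do not hold. A reader might infer that the VOS–Restasis comparison is biased; the test is done before randomization, so contamination falls equally on the arms in expectation. The primary discomfort endpoint and its power calculation do not use STT. A reader might also multiply 30% by 5 mm and expect a 1.5 mm loss. That keeps every affected subject in the trial, although the 10 mm ceiling removes many of them.

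**What to change.** In Protocol 8.1.1.4 and 8.2.1.1 and in SAP 3.1.4, add: *At Visit 1, after consent, record the time of the last eye drop of any kind in either eye; perform STT no sooner than 1 hour after it.* This reuses the minimum already set after study product.

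Reconcile Protocol 8.2.1.1 with SAP 3.1.4 so that the Visit 1 STT precedes every study-administered drop, including any used for dilation.

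The cost is one eCRF time field and a wait of up to about an hour for some subjects at Visit 1, with no added visit or procedure. If the sponsor intended to exclude anyone using tears on the day of Visit 1, Section 7.7.1 should say so.

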8. STUDY PROCEDURES

8.1 Description of Study Assessments

8.1.1 Dry Eye Disease Activity Assessments

The following assessments will occur as part of the evaluation of DED (see [Appendix 2](#)).

8.1.1.1 Symptom Assessment in Dry Eye (SANDE)

Subjects will be asked to subjectively rate the frequency and severity of their dry eye symptoms at Visits 2, 3, 4 and 5 using the SANDE. The total length of the line from “rarely” to “all the time” (frequency of symptoms) and from “very mild” to “very severe” (severity of symptoms) is 100 mm. Subjects will be asked to subjectively rate the frequency and severity of their symptoms (OU) by placing an “X” on the relevant horizontal line. The length of the line between the “rarely” or “very mild” starting point and the first point where the subject’s mark crosses each line will be measured and recorded in millimeters. This assessment is a general assessment of both eyes. There will not be a question for each individual eye. This assessment should be performed prior to assessing for AEs and prior to any other invasive visit assessment (see [Appendix 3](#)).

8.1.1.2 Visual Analogue Scale (VAS) Symptom Assessments

Individual Symptom Severity Assessments using VAS:

Subjects will be asked to rate their current symptoms (unrelated to study drug instillation) at Visits 2, 3, 4 and 5. The following six symptoms will be evaluated: Burning/Stinging, Foreign Body Sensation, Photophobia, Eye Pain, Eye Dryness, and Itching.

The subject will be asked to subjectively rate each of six ocular symptoms (OU) by placing a vertical mark on the horizontal line to indicate their level of discomfort. 0 corresponds to “No Symptoms” and 100 corresponds to “Severe Symptoms.” The linear dimension of the scale is measured in millimeters. This assessment is a general assessment of both eyes. There will not be a question for each individual eye. This assessment should be performed following SANDE, and prior to assessing for AEs and prior to any other invasive visit assessment (see [Appendix 4](#)).

8.1.1.3 Fluorescein Corneal Staining (FCS)

Corneal staining will be performed at Visit 2, 3, 4 and 5. This assessment should be performed after the Drop Discomfort Assessment at Visit 3, 4 and 5. Corneal staining assessment will be performed using methods developed by the NEI Dry Eye Workshop (see [Appendix 7](#)).

Evaluation Technique

NOTE: All steps in this procedure should be completed for the right eye (OD) prior to repeating the procedure for the left eye (OS).

- Place Slit-Lamp magnification at 10x (it is acceptable to use 16x if no reticle is used)
- Use a yellow barrier filter (Wratten or Tiffen #11 or #12)
- Place 5 μ L of non-preserved, 2% fluorescein into eye, gently touching the drop at the tip to the lower palpebral conjunctiva of the eye
- In order to thoroughly mix the fluorescein with the tear film, ask the subject to blink several times and move his/her eye around
- Wait 2.5 minutes to assess cornea
- Measure staining under Cobalt blue light (465 nm to 490 nm)
- Compare staining with the standard with scoring in each of 5 areas of the 5 corneal sections

Scoring system

- Grade each of 5 sections of cornea (superior, inferior, nasal, temporal, central)
- Provide grades for each of the 5 sections:
 - Grade by NEI scale (definition in [Appendix 7](#)) as 0, 1 (mild), 2 (moderate), or 3 (severe)
- Total score is obtained by summing each of the 5 sections of the cornea
 - NEI score will be from 0-15. (See [Appendix 7](#)).

